4. OBJECTIVES*

The goal of the study is to conduct a crowdsourced testing to examine the effects of source and presentation of e-cigarette educational messages among young adults who currently vape and do not vape. The objectives are to examine young adults' self-reported responses toward message source (expert vs. peer), message sidedness (one-sided vs. two-sided), and messages combining both (source x message sidedness) about anti-e-cigarette messages.

Aim 1: To determine the optimal message source and presentation type for young adult vapers and non-vapers to increase acceptance of e-cigarette education messages and e-cigarette harm perceptions.

H1. Vapers will report more optimal psychophysiological responses than peer and two-sided messages.

INVESTIGATOR STUDY PLAN - REQUIRED

H2. Non-vapers will report more optimal psychophysiological responses than expert and one-sided messages.

Please note that all procedures will be done with the appropriate personal protective equipment, which includes a mask and face shield for the researcher. Participants will be required to wear their mask for the entirety of the study.

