10. STUDY ENDPOINTS*

The primary outcome measures include psychophysiological responses (cognition, arousal, attention) and self-reported measures of e-cigarette harm message and source perceptions (message acceptance, harm perceptions, reactance, message liking, source trust, attitudes, behavioral intentions).

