11. PROCEDURES INVOLVED*

After providing informed consent, participants will be randomized to one of four experimental conditions in a 2 (Source: expert and peer) x 2 (Presentation: one-sided and two-sided) design. Data will be collected through iMotions, a psychophysiological data collection platform. We will track participants' eye movements using an eye-tracking device. We will assess heart rate and skin conductance with a sensor by attaching Velcro-strapped electrodes on the fingers of participant's nondominant hand. When the study begins, participants will complete pretest measures, view messages, during which they will be measured on their psychophysiological responses, and complete posttest measures. Messages (see Appendix-A) will be presented in a random order for at least 10 seconds. Between each message segment, a black screen and "get ready" screen will be presented for 10 seconds to return participants' heartrate and skin conductance levels to baseline. This meets the established amount of time (6 seconds) to collect heart rate and skin conductance.⁴⁵ This procedure will be repeated 18 times for the 18 messages. Finally, participants will complete measures on demographics, attitudes, and behavioral intentions. The entire procedure will take approximately 45 minutes. After completion, participants will be thanked and compensated \$50 for participation. Participants will be extensively debriefed about the hypothetical nature of the message source, the health harms of using any tobacco product, and information about the Massachusetts Tobacco Quitline with contact information. We will provide a consent form and verbally reiterate this information.

In order to minimize subject harm as a result of being shocked by static electricity from the sensors, room temperature will remain above 65 degrees when running participants as the colder,

INVESTIGATOR STUDY PLAN - REQUIRED

drier air is more likely to cause static shock. We will also follow all safety guidelines for the equipment. These include having participants wash their hands thoroughly, then use hand sanitizer, and then use an alcohol towelette to clean the finger the sensor will be placed. In addition, participants will be instructed to try to keep their hand still during the study to ensure the sensor does not move.

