12. DATA AND SPECIMEN BANKING*

NA

13. Data Analysis and Management*

Data will be collected through iMotions, a psychophysiological data collection platform. All data will be saved on a password protected computer on the UMass Chan Medical School server. Upon completion of data collection, all data will be de-identified and stored on the UMass Chan Medical School OneDrive.

Visual inspection of heart rate will be performed prior to statistical analysis to determine if a monophasic pattern resembling a U-shaped pattern is present. Each participant will receive a change in beats per minute (BPM) score based on the second before viewing (baseline) minus each second of the 10-second viewing of the message. Then, the BPM change score will be averaged per theme and compared for the greatest deceleration of heart rate, signifying greater attention to the messages in that theme category. Skin conductance will be analyzed similarly but compared for greatest acceleration, signifying greatest attention. Lastly, dwell time on the message using milliseconds will be calculated for the area of interest within the message. Longest dwell time will signify most visual attention for each message theme category. We will take the mean score for the self-report measures and rank the messages accordingly.

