All study data are collected using the iMotions 6.4 Biometric Research Platform, a secure, computer-based data collection platform. No self-report or psychophysiological data collected are directly linked to participant identifying information: self-report and psychophysiological data collected through iMotions are tracked using a unique, numeric study identifier that does not contain any personally identifying information. A monitor on the computer will track the participant’s eye movements and three sensors on the participant’s fingers will track heart rate and skin conductance. Each message will appear for ten seconds, which falls above the established amount of time needed (6 seconds) to collect heart rate and skin conductance levels for still messages. This will allow us to take into account baseline levels and time for heart rate and skin conductance to react. After each message, participants will answer the same measures included in the participant survey pertaining to responses toward the message and source, and

INVESTIGATOR STUDY PLAN - REQUIRED

perceived message effectiveness. This process will be repeated 18 times for each of the two message sidedness conditions, resulting in a total of 36 different messages seen by participants. Afterwards, participants will be asked to complete additional measures related to actual message effectiveness (e-cigarette attitudes, risk beliefs, intentions to vape).

Between each message sidedness condition, individuals will see a blank black screen for 10 seconds, then a black screen with the words “get ready” for five seconds followed by another black screen for 10 seconds to return heart rate and skin conductance back to baseline. All methods are consistent with accepted standards of psychophysiological measurement for media studies.

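### Attitudes and behavioral intentions are primary outcomes collected once, after all messages, but the only stated self-report analysis ranks messages, which ties on these scores; no comparison of randomised conditions is stated for them

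*Protocol*

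**What the plan says.** Protocol section 10 names as primary the psychophysiological responses and a set of self-report measures: "message acceptance, harm perceptions, reactance, message liking, source trust, attitudes, behavioral intentions".

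Two places describe when the last two are collected. Section 11, after describing the message series: "Finally, participants will complete measures on demographics, attitudes, and behavioral intentions". Section 26: "Afterwards, participants will be asked to complete additional measures related to actual message effectiveness (e-cigarette attitudes, risk beliefs, intentions to vape". By contrast, the ratings repeated during the series concern the message and its source, plus perceived effectiveness: "After each message, participants will answer the same measures included in the participant survey pertaining to responses toward the message and source".

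The stated analysis of self-report data is one sentence in section 13: "We will take the mean score for the self-report measures and rank the messages accordingly". The SAP adds a multi-attribute decision-making (MADM) dataset that holds responses to each message, labelled by source and presentation type, and uses it, merged with crowdsourced data, to rank messages. It justifies the sample size by the stability of the ranks of the three best messages.

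The objective in section 4 is a comparison of communication features: "message source (expert vs. peer), message sidedness (one-sided vs. two-sided), and messages combining both (source x message sidedness". Aim 1 asks for the best source and presentation type for vapers and non-vapers.

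The sections differ on exposure. Section 11 randomises each person to one of four source-by-presentation conditions and says "This procedure will be repeated 18 times for the 18 messages". Section 26 runs the series for both sidedness sets, "resulting in a total of 36 different messages seen by participants".

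**The concern.** A message can be ranked only on a score that varies between messages. Ratings taken after each message do. A score taken once at the end of the session does not: it reflects the whole set the person saw and attaches equally to every message in it.

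The section 13 sentence can be read in two ways. If it covers all self-report measures, it produces ties for attitudes and intentions. If it covers only the per-message ratings, no protocol analysis is stated for these two. On either reading, two named primary outcomes lack a stated estimate of a source or presentation effect, which is what section 4 asks for. If the gap is filled after the data are seen by ordering condition means, some condition will always come out on top, and nothing in the plan would show whether that is more than chance.

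**Working it through.** **Inputs.** 18 message pairs (Appendix A); 2 sources × 2 presentations (section 11 and SAP); 112 participants, 56 per vaping status (SAP). Assumed, because the documents do not state them: equal allocation, complete data, outcome in SD units, two-sided 5% level, 80% power.

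**The plan's own figure.** The SAP proposes 7 participants per message condition per vaping status.
- Four conditions: 7 × 4 × 2 = 56, which does not give 112.
- Eight cells: 7 × 8 × 2 = 112. Eight cells would arise from the four source directions in Appendix A × two presentations, but the SAP does not say so.
- With the four stated conditions, 56 / 4 = 14 per cell per stratum. This is used below.

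**Ties.** There are 18 × 2 × 2 = 72 combinations of message, presentation and source. Give each person's end-of-session score to every message that person saw, then average by message version.
- Section 11 (18 messages per person): 4 distinct means, each shared by 18 versions.
- Section 26 (36 messages per person): 2 distinct means, one per source, each shared by 36 versions. One-sided and two-sided versions cannot be separated at all.

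In neither case can a top three be formed.

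**What ordering the condition means would show.**
- Four cells of 14, no true difference: the expected range of four standard normal values is about 2.06, so the mean best-to-worst gap is 2.06 / √14 = 0.55 SD. Simulation (400,000 runs) agrees.
- In the same simulation, a condition truly 0.3 SD better than the other three ranks first 59% of the time; at 0.5 SD, 80%.
- Two source means of 28 each, no true difference: expected gap (2/√π) × √(1/28) = 1.128 × 0.189 = 0.21 SD.

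**Precision of a direct comparison, within one stratum of 56.**
- Main effect (28 v 28): SE = √(2/28) = 0.267; t(0.975, 52 df) = 2.007; half-width 0.54 SD. With source only (54 df) it is also 0.54 SD.
- Interaction as a difference of differences (four cells of 14): SE = √(4/14) = 0.535; half-width 2.007 × 0.535 = 1.07 SD.
- Detectable main effect: (1.960 + 0.842) × 0.267 = 0.75 SD.

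**Number of intervals.** 2 outcomes × 3 effects × 2 strata = 12. If these were independent (an assumption), the chance that at least one excludes zero under no effect is 1 − 0.95¹² = 46%. For the main effects alone, 8 intervals give 1 − 0.95⁸ = 34%.

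**The case against.** **The ranking could still yield something.** This stands in part. A reader might infer that the plan can produce no result at all for these outcomes. The documents do not support that: the MADM dataset carries source and presentation labels, so under section 11 it could order the four condition means, and under section 26 the two source means. What is missing is a stated contrast and a measure of uncertainty.

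**Section 13 does more than rank messages.** Correct. Heart rate, skin conductance and dwell time are compared by message theme. The point here is confined to self-report data.

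**No outcome has a stated comparison of conditions.** Also fair: the absence of a contrast is wider than these two measures. What is particular to them is that the one rule given for self-report data cannot discriminate between messages.

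**These are not the study's main focus.** Aim 1 names message acceptance and harm perceptions, and the hypotheses concern psychophysiology. That limits the weight of the point, but section 10 does list both outcomes as primary.

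**They might also be asked after each message.** The available text does not exclude it, and the pages that may hold the scales are not part of the reviewed text. The point rests on the timing that sections 11 and 26 describe, and both place these measures at the end.

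**Harm perceptions may be affected too.** A reader might infer this because section 26 puts risk beliefs at the end. It follows only if the two are the same measure, which the documents do not say.

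**Ties might break in practice.** Missing message data could make message means differ, but the differences would reflect who contributed and not the messages.

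**Conclusion.** The point holds for attitudes and behavioral intentions as the protocol describes their collection. Message ranking gives ties on them, and neither document states a contrast, model or interval for the effect of source or presentation on them. The most the stated methods could deliver is an order of four condition means or two source means. The best-to-worst gap expected by chance alone is about 0.55 SD for four cells of 14.

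The tie follows from the stated timing and needs no numerical assumption beyond complete message data. The 0.55 SD gap and the interval widths assume 56 per stratum split equally over four conditions. With four cells of 7 the half-widths would be 0.78 and 1.56 SD, but that contradicts the SAP's 56 per stratum. The four-condition, presentation and interaction figures apply only if each person sees one presentation type. The plan should be changed on this point, although the outcomes rated or recorded message by message are not affected by it.

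**What to change.** 1. Reconcile section 11 (18 messages, presentation assigned between persons) with section 26 (36 messages, both sidedness sets). This decides whether presentation can be compared on an end-of-session outcome at all.
2. In section 13 and the SAP, limit message ranking to ratings taken after each message.
3. For attitudes and behavioral intentions, compare the randomised conditions within each vaping stratum with a linear model on source, presentation and their interaction. Fit source only if each person sees both sidedness sets. Report differences with 95% confidence intervals.
4. Adjust for the pretest value if the same measure is taken then. Section 11 mentions pretest measures without listing them. The gain in precision cannot be computed from the documents, and the comparison is valid without it.
5. Name the main effects as the principal contrasts and label the rest, including the interaction, as exploratory. This reduces the 12 intervals to 8 principal ones; it does not remove multiplicity, so the text should say how the 8 will be read.
6. State the number per cell, and reconcile the SAP's 7 per message condition with 56 per stratum over four conditions.

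**Cost.** A few lines of protocol and SAP text; no new data, visits or scales. The downside is that the intervals will be wide, so the results will read as estimates and may not single out a best condition.

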16. RISKS TO SUBJECTS*

Risks to subjects involve experiencing a minor static shock as explained in #14 as well as being uncomfortable answering questions about tobacco use. Participants will be advised that they are free to refuse to answer any question that makes them feel uncomfortable. All observed or volunteered adverse events will be recorded through the IRB. Lastly, participants will be at

INVESTIGATOR STUDY PLAN - REQUIRED

some risk of breach of confidentiality, which is the case with most research studies. There are no known or suspected risks to pregnant women who may coincidentally be enrolled.

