27. PROVISIONS TO PROTECT THE PRIVACY INTERESTS OF SUBJECTS

All study activities will be conducted in a private setting. The collection of sensitive information about subjects is limited to the information necessary to conduct the research study. Subjects will be told that they can skip any question they wish.

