Cover Page for ClinicalTrials.gov

Document:

Statistical Analysis Plan

Official Study Title:

Responses to Message Source and Presentation Using Psychophysiology

Document Date:

January 17, 2024

Psychophysiological Testing

Study Design and Power Analysis:

We will assess which communication principles influence psychophysiological responses on visual attention, orienting response, and arousal to determine the features that can increase acceptance of e-cigarette education messages in young adults. Eligible participants will be randomly assigned to one of four experimental conditions in a 2 (Source: expert and peer) x 2 (Presentation: one-sided and two-sided) design. For the psychophysiological part of the Aim 1, we will recruit total 112 young adults (age 18 to 24) vapers and susceptible non-vapers. We will use stratified sampling, with n=56 for each vaping status. The estimation was based on Stevens et al.'s (2021) study. Based on simulations as in crowdsourcing study, participants per message condition gave stable ranks for the top 3 messages. We use a conservative approach and propose 7 participants per the message condition for each vaping status. I will use a multi-attribute decision-making (MADM) framework to produce a dataset containing data on participant response to each message with source + presentation type. I will merge crowdsourced and psychophysiological data to rank messages and determine optimal content. This technique has been used in our previous work. MADM provides a practical, transparent framework for considering data across multiple inputs, determining the relative importance of each attribute, and simultaneously evaluating detail at the attribute level and in a summary measure across all attributes using aggregate data.

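### Ranking messages on plain mean ratings loses precision once ratings are skipped; a participant-adjusted message mean is a cheap improvement with a modest gain

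*Protocol*

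**What the plan says.** Protocol section 10 lists "self-reported measures of e-cigarette harm message and source perceptions" among the primary outcome measures. Section 26 describes how they are collected: "After each message, participants will answer the same measures included in the participant survey". Section 11 has each participant randomized to one source-by-presentation condition and says "This procedure will be repeated 18 times for the 18 messages". Section 26 instead describes 36 messages covering both presentation types.

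On missing answers, section 27 states "Subjects will be told that they can skip any question they wish", and section 16 adds "Participants will be advised that they are free to refuse to answer any question that makes them feel uncomfortable".

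The self-report analysis in section 13 is one sentence: "We will take the mean score for the self-report measures and rank the messages accordingly". The SAP adds a multi-attribute decision framework working on aggregate data. It justifies the sample size by the stability of the top-3 ranks: "We use a conservative approach and propose 7 participants per the message condition for each vaping status" and "We will use stratified sampling, with n=56 for each vaping status". Neither document mentions a participant effect, a rule for missing answers, a minimum number of answers per message, or a sensitivity analysis.

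**The concern.** A rating reflects both the message and the person giving it. If everyone in a condition rates every message, the average rater level is the same for each message and drops out of the ranking. If some ratings are missing, each message has its own set of raters. Its raw mean then rises or falls with who happened to answer, although the message is the same.

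The number of raters is small, 7 or 14 per message depending on how conditions are counted, so one missing rating is not negligible. The sample size was chosen for stable top-3 ranks, and this source of instability acts on that quantity. It can be reduced without collecting anything more.

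**Working it through.** **1. Raters per message.** The SAP gives 7 per message condition and 56 per vaping status. Appendix A has 4 source directions; with 2 presentations that makes 8 message conditions, and 7 × 8 × 2 = 112, which reproduces the planned total. With the 4 randomized conditions of section 11, 7 × 4 × 2 = 56, which does not; 112 / (4 × 2) = 14 per cell. Both 7 and 14 are carried below.

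**2. One missing rating.** Removing one of n ratings that lies d SD from the mean of all n moves that message's mean by d/(n − 1) SD. For d = 1.5 this is 1.5/6 = 0.25 SD at n = 7 and 1.5/13 = 0.12 SD at n = 14.

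**3. Error variance, by formula.** Write a rating as message + rater + residual. If r of n raters answer for a message, the residual part of its error variance is (residual SD)²/r. The raw mean adds (rater SD)² × (1/r − 1/n), which is zero when r = n. The documents give no variances or skip rates, so assume residual SD 0.6 and rater SD 1.0. With n = 7 and 5% of ratings skipped independently, the average of 1/r is 0.1517:
- residual part: 0.36 × 0.1517 = 0.0546
- added by the raw mean: 1.0 × (0.1517 − 0.1429) = 0.0089 (unrounded inputs)
- ratio: 0.0089/0.0546, about 16% more

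At 2% skipped the same formula gives about 6%. At 5% with rater SD 0.6 it also gives about 6%. At 10% with rater SD 1.0 it gives about 33%. The formula treats rater levels as known and skips as independent, so it is a guide only.

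**4. Simulation.** Settings: 18 messages, message SD 0.3, residual SD 0.6, rater SD 1.0, skipping clustered by person, 1,500 runs per setting. Error is the root mean squared error (RMSE) of centred message means.

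| Raters, skipped | RMSE raw v adjusted | Extra variance, raw | Agreement with complete-data top 3, raw v adjusted |
|---|---|---|---|
| 7, 5% | 0.243 v 0.227 | (0.243/0.227)² − 1 = 15% | 87% v 92% |
| 7, 10% | 0.264 v 0.235 | (0.264/0.235)² − 1 = 26% | 79% v 87% |
| 14, 10% | 0.186 v 0.166 | (0.186/0.166)² − 1 = 26% | 81% v 89% |

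With nothing skipped the two methods agree exactly. At 2% skipped, or with rater SD 0.6, the gain in agreement is about 1 to 4 percentage points.

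**5. The benchmark that matters.** The complete-data top 3 is itself noisy at these sample sizes. Measured against the true top 3, with the same SDs and 7 raters, recovery is:
- 5% skipped: 57.6% raw v 59.2% adjusted, a gain of 1.6 points
- 10% skipped: 55.9% raw v 58.5% adjusted, a gain of 2.6 points
- nothing skipped: about 59 to 60% by either method

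With 14 raters and 10% skipped it is 64.5% v 66.6%, a gain of 2.1 points.

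**6. A second set of assumptions.** With residual SD 0.7, 7 raters and skipping concentrated in low scorers, true top-3 recovery is 54.9% v 55.8% at 2% skipped, 53.0% v 54.9% at 5%, and 51.3% v 54.9% at 10%. The direction is the same and the gain is still small (0.9, 1.9 and 3.6 points).

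**The case against.** **The gain is small.** This stands. Sampling noise with 7 raters costs far more than skipping does: even complete data recover only about 59 to 60% of the true top 3. A reader might infer that skipping alone makes the top 3 untrustworthy; the figures do not support that.

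**The documents do not show selective skipping.** This also stands. A reader might infer that vapers, or harsh raters, will skip more. Section 5 says that young adults, especially vapers, may avoid or reject the messages; it does not say they will leave rating items blank. The discomfort clause in section 16 follows a sentence about questions on tobacco use, not message ratings. Messages appear in random order, so stopping early favours no particular message. A person who skips the same item for every message leaves the raters balanced and the ranks unaffected. Only scattered skipping matters, and its rate is unknown.

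**Section 13 does not say that the mean is over whoever answered.** True. It could mean averaging items into a scale score, in which case one skipped item need not lose the rating. But no rule is given for either step, and a mean of the available answers is the plain reading.

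**Self-report is only part of the result.** H1 and H2 in section 4 concern psychophysiological responses, and the SAP merges several inputs, including crowdsourced data. The effect on the final ranking is diluted by an unknown amount. Heart rate, skin conductance and dwell time are untouched by skipped questions. Self-report measures are nevertheless listed as primary outcomes.

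**A careless model would do harm.** Under section 11, participants are nested within conditions. Fixed participant terms in a model pooled over conditions would absorb the source and presentation differences that the study is meant to compare. The fix must avoid this.

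**Conclusion.** The point holds as one of precision. Skipping is allowed, the stated method is a plain mean, and raters per message are few, so missing ratings let rater level leak into the message ranking. Under the assumed SDs with 7 raters, the raw mean carries about 15% more error variance than an adjusted mean at 5% skipped and about 26% at 10%, while true top-3 recovery improves by only about 2 to 3 percentage points. The benefit shrinks with fewer skips or more similar raters and vanishes if nothing is skipped. All these sizes rest on assumed variances and skip rates. The documents establish neither a bias linked to vaping status nor a material threat to the study's overall conclusion. The change is worth making because it costs little and fixes the handling of missing ratings before the ranks are seen.

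**What to change.** In section 13 and the SAP, for the self-report measures collected after each message, replace the raw mean by the estimated message mean from a model with message terms and a participant intercept. Fit it to all answered ratings within each vaping status, keeping the ratings of people who skip some items or stop early. Either fit it separately within each source-by-presentation condition, or use a random participant intercept with condition and message-by-condition terms. Do not use fixed participant terms across conditions. Rank on the estimated means and report the number answering for each message.

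The end-of-session attitudes and behavioral intentions should be left out of this model: they are collected once and cannot carry a message term.

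First reconcile section 11 (18 messages, one presentation per participant) with section 26 (36 messages, both presentations), because the model depends on whether presentation varies between or within participants.

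The cost is a short addition to each document and one standard model per measure, with no new data. The model assumes that skipping is ignorable given the participant, and it reduces the movement in ranks without removing it. Within a condition, the ranks equal the planned ones if nothing is skipped.
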